12.4.2.4. Quarterly and External Safety Review: The Tazemetostat Safety Committees

Monitoring of secondary primary malignancies is a pharmacovigilance function. All potential safety signals and AESIs will be fully evaluated in Quarterly Safety Review (QSR) meetings and in the External Safety Committee (ESC). Monitoring for potential safety signals, AESI and other safety concerns will also be evaluated during SRC and by the IDMC.

The QSR is composed of internal Epizyme subject matter experts. It is a cross-functional workgroup whose mission is to provide internal review of aggregate safety data from Epizyme global clinical and safety databases. The core committee is composed of the Epizyme Chief Medical Officer (CMO), Medical Monitor(s), Head of Nonclinical Safety, Vice President (VP) Pharmacovigilance, VP Clinical Operations, and VP Regulatory Affairs.

The primary objective of the QSR is to provide a routine, systematic, internal review of new and aggregate safety information, and to escalate newly identified concerns or issues to executive management and regulatory authorities, as applicable.

The QSR also serves in the review and adjudication of urgent safety findings identified during the course of Epizyme clinical trials and as the escalation path, as applicable.

The ESC is composed of independent oncology medical consultants; one of which serves as Chair. The ESC meets quarterly to review new data, or ad hoc.

The purpose of the ESC is to provide independent review of clinical data for the purposes of identifying and evaluating secondary malignancy safety signals from Epizyme sponsored clinical trials. The ESC also monitors the data of those study subjects who have experienced the tazemetostat AESIs, namely T-LBL/T-ALL, MDS, AML, and other myeloproliferative malignancies such as MPN.

Outcomes from ESC meetings may include, but are not limited to, the identification of new AESI and/or potential risk factors, the need for additional non-clinical studies or data analyses, proposals for risk mitigation measures and confirmation or revision of the tazemetostat benefit-risk. The ESC will make recommendations in the event of an AESI safety concern. Epizyme will implement recommendations which may include suspension of enrollment, protocol amendment and communication to health authorities.

12.4.4. Grading and Severity

The severity of all AEs and SAEs, including appropriate laboratory values, will be graded utilizing the CTCAE v5.0 (National Institutes of Health, November 27, 2017).

In the event that an AE is not covered by the CTCAE, the assessment of severity will be determined by using the CTCAE general guideline, as follows:

Grade 1:	Mild; asymptomatic or mild symptoms; clinical or diagnostic observations only; intervention not indicated.
Grade 2:	Moderate; minimal, local, or noninvasive intervention indicated; limiting age- appropriate instrumental ADL. ^a
Grade 3:	Severe or medically significant but not immediately life-threatening; hospitalization or prolongation of hospitalization indicated; disabling; limiting self-care ADL. ^b
Grade 4:	Life-threatening consequences; urgent intervention indicated.
Grade 5:	Death related to AE.

Abbreviations: ADL = activities of daily living; AE = adverse event.

^a Instrumental ADL refer to preparing meals, shopping for groceries or clothes, using the telephone, managing money, etc

^b Self-care ADL refer to bathing, dressing, and undressing, feeding self, using the toilet, taking medications, and not bedridden.

An AE that is assessed as severe should not be confused with an SAE. Severity is a category used for rating the intensity of an event (as in ‘mild’, ‘moderate’, or ‘severe’); both AEs and SAEs can be assessed as severe. An event is described as ‘serious’ when it meets one of the pre-defined outcomes as described in [Section 12.4.1.2](#) which are based on patient/event outcome or action criteria associated with events that pose a threat to a subject’s life or functioning.

12.5. Relationship to Study Drug

A qualified Investigator must make the determination of relationship to study drug for each AE. The Investigator should decide whether, in his or her medical judgment there is a reasonable possibility that the event may have been caused by tazemetostat.

The following should be considered when assessing the relationship of an AE to study treatment:

- Temporal relationship of the onset of the event to the first dose of study drug
- The course of the event, considering especially the effect of discontinuation of study treatment or the reintroduction of study treatment, as applicable
- Whether the event is known to be associated with the study treatment or with other similar treatments
- The presence of risk factors in the study subject known to increase the occurrence of the event
- The presence of non-study treatment-related factors that are known to be associated with the occurrence of the event.

Investigators must also systematically assess the causal relationship of AEs to the study drug using the following definitions (the decisive factor being the temporal relationship between the AE and administration of the study drug):

- **Probable:** A causal relationship is clinically/biologically highly plausible, there is a plausible time sequence between onset of the AE and administration of the study drug, and there is a reasonable response on withdrawal.
- **Possible:** A causal relationship is clinically/biologically plausible and there is a plausible time sequence between onset of the AE and administration of the study drug.
- **Unlikely:** A causal relationship is improbable, and another documented cause of the AE is most plausible.
- **Unrelated:** A causal relationship can be definitively excluded, and another documented cause of the AE is most plausible.

12.6. Recording Adverse Events

Adverse events spontaneously reported by the subject and/or in response to an open question from the study personnel or revealed by observation will be recorded during the study at the investigational site. Clinically insignificant changes in laboratory values, BP, and pulse need not be reported as AEs. However, abnormal values that constitute an SAE or lead to discontinuation of administration of study drug must be reported and recorded as an AE. Information about AEs will be collected from signing of the consent form until the end of the study. Serious Adverse Event information will be collected from signing of the informed consent until 30 days following the last dose of study drug and for related SAEs, until resolution. The AE term should be reported in standard medical terminology when possible. For each AE, the Investigator will evaluate and report the onset (date and time), resolution (date and time), intensity, causality, action taken, serious outcome (if applicable), and whether or not it caused the subject to discontinue the study.

Intensity will be assessed according to the CTCAE v5.0 or [Section 12.4.4](#).

Should a pregnancy occur, it must be reported and recorded on the Sponsor's pregnancy form. Pregnancy in itself is not regarded as an AE unless there is a suspicion that a study drug may have interfered with the effectiveness of a contraceptive medication. Study IMP will stop immediately for female subjects who become pregnant.

The outcome of all pregnancies (spontaneous miscarriage, elective termination, normal birth, or congenital abnormality) will be followed up (assuming consent) and documented even if the subject was discontinued from the study.

All reports of congenital abnormalities/birth defects are SAEs. Spontaneous miscarriages should also be reported and handled as SAEs. Elective abortions without complications should not be handled as AEs.

12.7. Reporting Adverse Events

All AE and SAEs (related and unrelated) will be recorded from the signing of consent form until the end of the safety reporting period (or until screen failure, 30 days following the end of treatment exposure or initiation of an investigational agent or cytotoxic chemotherapy, whichever occurs first). Any SAEs considered possibly or probably related to the study drug and discovered by the Investigator at any time after the study should be reported. All SAEs must be

reported to the Sponsor within 24 hours of the first Investigator awareness of the event. The Investigator must complete, sign and date the SAE pages, verify the accuracy of the information recorded on the SAE pages with the corresponding source documents, and send a copy to the Sponsor.

Additional follow-up information, if required or available, should all be reported to the Sponsor. Epizyme, Inc. following the same reporting timeline as the initial report, and this should be completed on a follow-up SAE form and placed with the original SAE information and kept with the appropriate section of the eCRF and/or study file.

12.8. Reporting of Serious Adverse Events

All SAEs will be reported to the Sponsor within 24 hours of the Investigator becoming aware of the event. The Investigator must promptly notify the Sponsor or its designee of all SAEs in order that the legal obligations and ethical responsibilities of the sponsor or its designee are met.

The Sponsor has a legal responsibility to notify both the local regulatory authority and other regulatory agencies about the safety of the study drug under clinical investigation. The Sponsor and its designee will comply with country specific regulatory requirements relating to safety reporting to the regulatory authority, IRB/EC/CEC, and Investigators.

Any SAE that is unexpected (not consistent with the applicable product information) and considered related to the study treatment by the Investigator-or the Sponsor, meets the definition of a SUSAR. SUSARs are prepared for expedited reporting according to local regulatory requirements and are forwarded to Investigators as necessary. The Sponsor is legally obligated to report SUSARs to the regulatory authorities within 7 days for fatal or life-threatening events or 15 days for all other events.

An Investigator who receives an Investigator safety report describing a SAE(s) or other specific safety information (eg, summary or listing of SAEs) from the sponsor will file it with the IB and will notify the IRB/EC/CEC, if appropriate according to local requirements.

12.9. Reporting of Pregnancy

Pregnancy will not be considered an SAE. Any report of pregnancy recorded for any female subject, or a female partner of a male subject should be reported. To ensure subject safety, each pregnancy must be reported to the Sponsor or its designee within 2 weeks of learning of its occurrence using a clinical trial Pregnancy Report Form. A Pregnancy Report Form should be completed and submitted by email and/or fax to the Sponsor or its designee.

The pregnant female subject must be withdrawn from the study. Every effort should be made to gather information regarding the pregnancy outcome until 8 weeks post-partum. It is the responsibility of the Investigator to obtain all pregnancy information.

Pregnancy complications and elective terminations for medical reasons must be reported as an AE or SAE. Spontaneous abortions must be reported as an SAE.

Any SAE occurring in association with a pregnancy brought to the Investigator's attention after the subject has completed the study and considered by the Investigator as possibly related to the study treatment, must be promptly reported to the Sponsor.

The Investigator also must attempt to collect and report to the Sponsor or its designee pregnancy information on any female partner of male study subjects who become pregnant while the subject is enrolled in the study.

12.10. Reporting of Adverse Events of Special Interest

All potential and identified AESIs, irrespective of their relationship to study treatment, must be reported as soon as possible, but no later than 24 hours from when the Investigator becomes aware of the event.

12.11. Reporting of Special Situations: Overdose, Misuse, Abuse, or Medication Error

Report the special situation(s) of overdose, misuse, abuse, and/or medication error (described in Section 9.3.1) using one of the following sets of instructions according to whether the special situation occurred without any associated AEs, with an associated non-serious AE, or with an associated SAE:

Special situation(s) without associated AE(s):

- Report to Epizyme using a paper Special Situations Form following the procedures for reporting SAE (Section 12.8).

Special situation(s) with an associated non-serious AE:

- Enter the non-serious event on the AE eCRF and mark the SAE field, “no”. SAE related narrative fields should not be completed.
- Report to Epizyme using a paper Special Situations Form following the procedures for reporting SAE (Section 12.8).

Special situation(s) with an associated SAE:

- Complete the AE eCRF per protocol for the associated SAE term ONLY (Special situations are not adverse event terms in and of themselves); complete eCRF SAE fields.
- Report to Epizyme using both a paper Special Situations Form and a paper Serious Adverse Event Form following the procedures for reporting SAE (Section 12.8).

13. STATISTICS

Summaries of continuous variables will present the number of subjects included in the analysis (N), the mean and standard deviation (SD), the median, the minimum, and the maximum statistics. Counts and percentages will be presented in summaries of categorical variables. The denominator for each percentage will be the number of subjects in the population unless otherwise specified. In general, missing data will not be imputed unless otherwise specified.

All disposition, baseline demographics and disease characteristics will be descriptively summarized for the Safety population

Analyses will be done separately for each study part and overall.

13.1. Study Design Considerations

13.1.1. Determination of Sample Size

A total of 12 subjects per study part is adequate to describe the effect of CYP3A4 inhibition by itraconazole or induction by rifampin on the steady state PK of tazemetostat.

A point estimate and associated 90% confidence interval on the magnitude of the effect of the perpetrator drugs on the PK of the victim drugs will be provided. The default no effect boundary of 80 – 125% for the 90% confidence interval for an effect size will be used as a reference. This is equivalent to a hypothesis test with a null hypothesis that there is a nonzero effect and alternative of no effect. If the 90% confidence interval for any effect tested in this study falls completely within 80 – 125%, it will be concluded that no significant differences are present.

The sample size calculation is based on the underlying assumption that the within subject coefficient of variation (CV) is 30%, a two-sided alpha level of 0.05, the underlying within-subject correlation of subsequent measurements of the same PK parameter and geometric mean ratio. If the geometric mean ratio of itraconazole is 1.06 or the geometric mean ratio for rifampin is 0.94 and subsequent measurements of tazemetostat AUC have a correlation of at least 0.80, this test is powered at 88% or higher.

Calculations were performed using the Paired t-test for the Equivalence of Log-Normal Means (Multiplicative Model) in nQuery version 8.0.

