5.3. Study Rationale

Tazemetostat is metabolized primarily by CYP3A4. Inhibition or induction of CYP3A4 in vivo is expected to result in increased or decreased systemic exposure to tazemetostat respectively. Therefore, Part 1 of this study will determine the effect of a strong CYP3A4 inhibitor, itraconazole, on tazemetostat PK. Likewise, Part 2 of the study will determine the effect of a strong CYP3A4 inducer, rifampin, on tazemetostat PK.

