4.2. SAMPLE SIZE

The sample size was determined based on feasibility considerations. Approximately 40 subjects will be enrolled in the study assuming about a 40% drop out rate to achieve 12 subjects per study part for a total of 24 completed subjects. Subjects will complete either Part 1 or Part 2, but not both.

Subjects who require a tazemetostat dose interruption or reduction during Cycle 1 of either Part 1 or Part 2 will be replaced. During Cycle 1, subjects who miss two or more consecutive tazemetostat/itraconazole/rifampin doses or more than three tazemetostat/itraconazole/rifampin doses in total will be replaced. Subjects who miss two or more consecutive PK blood sample collections during either part of Cycle 1 will be replaced. Subjects that require replacement will be discontinued from study treatment.

A total of 12 subjects per study part is adequate to describe the effect of CYP3A4 inhibition by itraconazole or induction by rifampin on the steady state PK of tazemetostat.

A point estimate and associated 90% confidence interval on the magnitude of the effect of the perpetrator drugs on the PK of the victim drugs will be provided. The default no effect boundary of 80 – 125% for the 90% confidence interval for an effect size will be used as a reference. This is equivalent to a hypothesis test with a null hypothesis that there is a nonzero effect and alternative of no effect. If the 90% confidence interval for any effect tested in this study falls completely within 80 – 125%, it will be concluded that no significant differences are present.

The sample size calculation is based on the underlying assumption that the within subject coefficient of variation (CV) is 30%, a two-sided alpha level of 0.05, the underlying within-subject correlation of subsequent measurements of the same PK parameter and geometric mean ratio. If the geometric mean ratio of itraconazole is 1.06 or the geometric mean ratio for rifampin is 0.94 and subsequent measurements of tazemetostat AUC have a correlation of at least 0.80, this test is powered at 88% or higher.

Calculations were performed using the Paired t-test for the Equivalence of Log-Normal Means (Multiplicative Model) in nQuery version 8.0.

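### The 30% CV behind the 88% power is labelled within-subject, but the figure reproduces only if 30% is the CV of a single AUC measurement; the stated alpha and null do not match the 90% CI rule either

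*Protocol*

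**What the plan says.** Protocol 13.1.1 plans for 12 completers per part. The decision rule is a 90% confidence interval for the geometric mean ratio lying wholly within 80–125%. The section describes this rule as follows: "This is equivalent to a hypothesis test with a null hypothesis that there is a nonzero effect and alternative of no effect".

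The power statement rests on "the underlying assumption that the within subject coefficient of variation (CV) is 30%, a two-sided alpha level of 0.05", with geometric mean ratios of 1.06 (itraconazole) and 0.94 (rifampin). It concludes that if "subsequent measurements of tazemetostat AUC have a correlation of at least 0.80, this test is powered at 88% or higher". The method is given next: "Calculations were performed using the Paired t-test for the Equivalence of Log-Normal Means (Multiplicative Model) in nQuery version 8.0".

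SAP 4.2 repeats these paragraphs but opens with a different basis: "The sample size was determined based on feasibility considerations". Neither document cites a source for the 30% or the 0.80.

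**The concern.** A within-subject CV describes the scatter of repeated measurements around a subject's own mean. Between-subject variance has already been removed from it. The correlation between a subject's two AUCs measures the share of total variance that lies between subjects. It reduces the variance of the paired difference only when the starting CV is that of a single measurement, between plus within. Applying 0.80 to a CV that is truly within-subject removes the between-subject part twice.

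A reader who takes the label at face value will believe that 12 completers tolerate a within-subject CV of 30%. The calculation allows less than half of that.

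Two further statements in the same text do not match the rule:

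- A 90% CI rule is two one-sided tests at 0.05 each. Taken literally, "a two-sided alpha level of 0.05" means 0.025 per side.
- The null for this rule is a ratio at or beyond 0.80 or 1.25, not any nonzero effect. The planning ratios of 1.06 and 0.94 are themselves nonzero effects, yet power is computed with them under the alternative.

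**Working it through.** **Inputs (protocol 13.1.1, SAP 4.2).** n = 12 (11 degrees of freedom); limits ln 0.80 and ln 1.25; ratios 1.06 and 0.94; CV 30%; correlation ρ = 0.80. I take ρ on the log scale and equal variances in the two periods; the documents state neither.

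**Log-scale SD for a 30% CV.** σ = √ln(1 + 0.30²) = 0.2936.

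**SD of the paired log difference under three readings of the 30%.**

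- A. CV of a single measurement: σ√(2(1 − 0.80)) = 0.2936 × √0.4 = 0.1857.
- B. Within-subject CV, as labelled: σ√2 = 0.4152. The correlation plays no part.
- C. CV of the paired difference: σ = 0.2936. The correlation again plays no part.

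**Exact power of the paired two one-sided tests**, integrating over the distribution of the sample variance:

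| Reading | Alpha per side | Power at 1.06 | Power at 0.94 |
|---|---|---|---|
| A, single measurement with ρ = 0.80 | 0.05 | 89.1% | 87.9% |
| A | 0.025 | 79.7% | 78.0% |
| B, within-subject | 0.05 | 14.5% | 14.3% |
| C, paired difference | 0.05 | 50.1% | 49.0% |

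A simulation of 400,000 runs at 0.05 per side agrees: 89.2% / 88.0% for A, 14.5% / 14.3% for B, 50.1% / 49.1% for C.

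Only reading A at 0.05 per side uses every stated input and returns the stated 88%. This also shows that the two-sided 0.05 was not applied literally, since A at 0.025 per side falls about ten points short.

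**Within-subject CV implied by reading A.** σ_w² = σ²(1 − 0.80) = 0.0862 × 0.20 = 0.0172, so CV_w = √(e^0.0172 − 1) = 13.2%.

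**Reverse check.** If 30% were truly within-subject and ρ were 0.80, the single-measurement CV would be √(e^(0.0862/0.20) − 1) = 73.4%.

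**Effect on precision.** The expected 90% CI is the estimate times or divided by exp(t × SD/√12), with t(0.95, 11) = 1.796.

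- A: exp(1.796 × 0.1857/3.464) = 1.10.
- B: exp(1.796 × 0.4152/3.464) = 1.24.

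**Effect if there is an interaction.** True ratios of 1.5 and 2 are my illustrative assumptions. The chance that the 90% CI lies wholly above 1.25 is 94% and over 99.9% under A, and 41% and 98% under B.

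**False no-effect rate.** At a true ratio of 0.80 or 1.25 it is 5.0% (A), 3.3% (B) and 5.0% (C), so it never exceeds 5%.

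**The case against.** The best defence is that no computed number is shown to be wrong. The 88% reproduces, the paragraph names the correlation as an input and makes the power conditional on it, and the paired log-normal procedure is named. A statistician can therefore recover what was done. That stands, and it is why a wrong label is the likelier explanation. It does not rescue the text: within-subject CV is a technical term with another meaning, and the stated power does not follow from it.

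A second objection is that the documents alone cannot settle whether the label or the power is wrong. This also stands. What they establish is that the two cannot both be right. The 14% power and the 1.24 interval factor are contingencies that apply only if the source shows a true within-subject 30%.

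Third, ρ could be on the raw scale. Power under reading A is then 90.0% / 88.9% and the implied within-subject CV 13.0%, so the conclusion does not move. The 73% in the reverse check becomes about 84%.

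Fourth, the alpha and null points are loose wording, since the 80–125% boundary and the 90% CI rule sit beside them and govern. I agree, and give them less weight.

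Finally, little depends on the figure. The SAP rests n on feasibility, and the protocol says "A total of 12 subjects per study part is adequate to describe the effect of CYP3A4 inhibition by itraconazole or induction by rifampin". Protocol 5.3 says that "Inhibition or induction of CYP3A4 in vivo is expected to result in increased or decreased systemic exposure to tazemetostat respectively", whereas the power figure applies only near a ratio of 1. All of this limits the weight of the point. A published power claim should still follow from its stated assumptions.

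**Conclusion.** The point holds and is minor. The stated 88% does not follow from a within-subject CV of 30%. It follows from a single-measurement CV of 30% with correlation 0.80, tested at 0.05 per side, which means a within-subject CV of about 13%. The label is probably the error and the software calculation correct. Only the source of the 30% can confirm that, and the documents do not give it.

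The consequence is confined to the planning statement. The point estimate, its 90% CI (which uses the observed variance), the 80–125% reference and patient safety do not change, and the false no-effect rate stays at or below 5% under every reading. For a large interaction the label matters little. These figures assume 12 completers per part, equal variances in the two periods and a log-scale correlation.

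**What to change.** Trace and cite the source of the 30% and the 0.80. If the 30% is a single-measurement CV, replace the power sentences in protocol 13.1.1 and SAP 4.2 with:

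> Assuming a CV of 30% for a single AUC measurement (between plus within subject) and a correlation of at least 0.80 between a subject's two measurements (implied within-subject CV about 13%), 12 completers per part give about 88% power or higher at geometric mean ratios of 1.06 or 0.94, using two one-sided tests at 0.05 each (90% CI). The null hypothesis is a ratio outside 80–125%.

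If the source shows that the 30% is truly within-subject, remove the correlation, restate the power as about 14%, and rest the 12 completers on feasibility and precision (expected 90% CI about the estimate times or divided by 1.24).

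The cost is one paragraph in each document and a check of two inputs. No patients, visits or samples are added, and the analysis is unchanged.
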